#### 8.8.4.4. Dose Response

If Part 2 enrolls, dose-response may be evaluated, if the data warrants, based on the pairwise comparisons of pre-dose/trough values for plasma VAP-1/SSAO activity ( $A_{avg}$  and  $A_{min}$ ) and methylamine concentration ( $C_{avg}$  and  $C_{max}$ ) from the ANCOVA models specified above (Section 8.8.4.3). In addition, pre-dose/trough VAP-1/SSAO activity ( $A_{avg}$  and  $A_{min}$ ) and methylamine concentration ( $C_{avg}$  and  $C_{max}$ ) will also be plotted by treatment group based on values, change from baseline, and percent change from baseline.

Dose response will also be evaluated using a REML based MMRM. The dependent variable will be the percent change (separately for change) from baseline for plasma VAP-1/SSAO activity and methylamine. The model will include the following fixed effects:

- Treatment group (4 levels: placebo [0 mg], 4 mg, 10 mg, 20 mg)
- Categorical time
- Treatment group by time interaction
- Baseline value

An unstructured covariance model will be used. If the computational algorithm fails to converge, the following structures will be executed: heterogeneous Toeplitz, heterogeneous First-Order Autoregressive [AR (1)], heterogeneous compound symmetry (HCS), Toeplitz, AR(1), and compound symmetry (CS). The covariance structure converging to the best fit, as determined by Akaike's information criterion (AIC, the smaller the AIC value the better the model fit), will be used. If the model converges with an unstructured covariance matrix, the Kenward and Roger method will be used to calculate the denominator degrees of freedom for the test of fixed effects. If a structured covariance is used, then a robust sandwich estimator will be utilized for estimating the variance of the treatment effect estimate.

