9.4.3.2. Change from Baseline in Plasma VAP-1/SSAO Activity

A secondary efficacy endpoint is change from baseline in plasma VAP-1/SSAO activity with 12 weeks of treatment in patients treated with either TERN-201 or matching placebo. The change and percent change from baseline in plasma VAP-1/SSAO amine oxidase activity in each TERN-201 group will be compared with placebo separately at each post baseline visit, without controlling for any family-wise error rate (overall type I error), using MMRM (mixed model repeated measures) model with treatment group, visit, and treatment group by visit interaction as factors and baseline value as covariate.

Change and percent change from baseline plasma VAP-1/SSAO amine oxidase activity will be listed and summarized with descriptive statistics including arithmetic and geometric mean, median, standard deviation, arithmetic and geometric CV, minimum, and maximum. Exposure-response and dose-response relationships of orally administered TERN-201 will also be assessed as applicable (exploratory endpoints).

Exposure-response and dose-response analysis may be produced if Part 2 of the study is enrolled, as applicable. The change and percent change from baseline in plasma VAP-1/SSAO activity will be compared between the different TERN-201 dose groups and placebo using an analysis of covariance (ANCOVA) model with the treatment group as a factor and baseline values as a covariate. Corresponding least square mean treatment differences with 2 sided 95% confidence limits will be computed for each pairwise comparison.

Further details on the analysis models will be provided in the SAP.

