#### **2.2.4. Treatment Assignment, Blinding, and Randomization Methodology**

Patients will be randomized to TERN-201 or placebo using an Interactive Web Response System (IWRS). Before the study is initiated, the log-in information and directions for the IWRS will be provided to each site.

Up to approximately 80 patients will be enrolled in this study. In Part 1, approximately 30 patients will be randomized at a ratio of 2:1 to receive TERN-201 10 mg (n = 20) or matching

placebo (n = 10). In Part 2, if initiated, up to approximately 50 patients will be randomized at a ratio of 2:1 to receive TERN-201 4 mg (n = 20), and/or 20 mg TERN-201 (n = 20), or matching placebo (n = 10). Randomization will be stratified by Screening MRI cT1 values  $\leq$  900 ms versus  $>$  900 ms.

The randomization codes will be provided to bioanalytics to allow for the exclusion of placebo patients from the PK assay. Bioanalytics will not disclose the randomization code or the results of their measurements until the trial is officially unblinded.

Emergency unblinding procedures are outlined in Section 6.4.1 of the study protocol and in the unblinding plan.

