## **8. EFFICACY ANALYSES**

### **8.1. Adjustments for Covariates**

For comparison of treatment groups with respect to change and percent change from baseline, analysis of covariance (ANCOVA) and restricted maximum likelihood (REML) based mixed model repeated measures (MMRM) models will be used. The corresponding baseline value will be used as a covariate in the model.

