#### **8.8.4.3. Statistical Methods for PD Parameters**

Plasma PD parameters will be summarized by treatment group using descriptive statistics (number of non-missing observations, arithmetic mean, SD, median, Q1, Q3, minimum, maximum, geometric mean, and geometric CV%).

For the calculation of summary statistics, all NR and not calculated (NC) values in a data series will be set to missing.

Analyses of pre-dose/trough values for plasma VAP-1/SSAO activity ( $A_{avg}$  and  $A_{min}$ ) and methylamine ( $C_{avg}$  and  $C_{max}$ ) at Week 0/Day 1, Week 6, and Week 12 will be carried out using an ANCOVA model with the PD parameter as the dependent variable including treatment group as a fixed effect and baseline VAP-1/SSAO activity or methylamine concentration as a covariate. The model will be carried out separately for the PD parameter based on the VAP-1/SSAO activity and methylamine value, change from baseline, and percent change from baseline. The estimates of LS means, SE, and 90% and 95% CIs will be presented by treatment group. Estimates of the LS mean difference for each pairwise comparison will be presented with associated the standard error of the difference, and 90% and 95% CIs of the difference.

The distribution of parameter values will be evaluated visually for normality assumptions. If normality assumptions are violated, first the data will be natural log transformed and the log transformed data evaluated for normality. If the log transformed data are normally distributed, the same ANOVA model described above will be used.

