#### **8.10.1.1. Corrected T1 (cT1)**

cT1 related to the amount of extracellular fluid present in the liver parenchyma. cT1 is derived from T1 and T2\* maps. T1 is a measure of the longitudinal (spin-lattice) relaxation time, measured in milliseconds (msec), of a given substance. The T1 of a tissue depends on its free water content, which relates to the proportion of the extracellular fluid in the tissue.

Proton-dense tissues with a low water content, such as fat, have very short T1 values, while tissues with a high water content, such as muscle and the spleen have much longer T1 values. When tissue is inflamed or scarred (fibrotic), changes in the structural organization of the tissue, due to tissue remodeling, mean that the water content increases, leading to longer T1 values.

cT1 is measured in milliseconds (msec). The cT1 metric is calculated from all pixels with whole slice ROIs placed on the cT1 parametric map. The cT1 metric is displayed as a median and IQR, the median will be used in all analyses.

Analyses of cT1 will be based on the Efficacy Analysis Set. Descriptive statistics of the cT1 values, change from baseline, and percent change will be summarized by treatment group and visit.

Analyses of change (and separately percent change) from baseline will be carried out using an ANCOVA model at each scheduled visit with change (and separately percent change) from baseline as the dependent variable including treatment group and randomization strata as fixed effects and baseline as a covariate.

The estimates of least-square (LS) means, standard errors (SE), and 90% and 95% CIs will be presented by treatment group. Estimates of the LS mean difference for each pairwise comparison will be presented with associated the standard error of the difference, and 90% and 95% CIs of the difference.

The primary analysis of change (and separately percent change) at Week 12 will be carried out using available observed data only, without imputation for missing data. The same ANCOVA

model will be used to present the last on treatment value for Week 12, to be labelled as “Week 12/End of Treatment”. For patients who complete Week 12, the Week 12 value will be used. For patients who do not complete treatment, the last value on treatment will be used.

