### **8.10.8. Dose Response**

Dose-response analyses for ALT, AST, GGT, cT1, MRI-PDFF, CK-18 (M30 and M65), PRO-C3, C3M, and PROro-C3/C3M ratio will be performed using the same methodology specified in [Section 8.8.4.4](#).

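### The dose-response MMRM omits the cT1 randomization stratum that the SAP's ANCOVAs of the same endpoints include, and no reason is given

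*SAP*

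**What the plan says.** SAP 2.2.4: "Randomization will be stratified by Screening MRI cT1 values", with two levels split at 900 ms.

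Two ANCOVA specifications use that factor. The cT1 model in SAP 8.10.1.1 is fitted "including treatment group and randomization strata as fixed effects and baseline as a covariate", and SAP 8.8.3 specifies the same terms for VAP-1/SSAO activity and methylamine. Later parts of 8.10 reuse the 8.10.1.1 model for MRI-PDFF, elastography, liver function tests and biomarkers.

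Two other specifications do not use it:

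- SAP 8.8.4.4, dose-response MMRM: "The model will include the following fixed effects", followed by four terms (treatment group, categorical time, their interaction, baseline value). On the outcome: "The dependent variable will be the percent change (separately for change) from baseline for plasma VAP-1/SSAO activity and methylamine". SAP 8.10.8 says that the efficacy dose-response analyses "will be performed using the same methodology specified in" Section 8.8.4.4.
- SAP 8.8.4.3, ANCOVA of PD parameters: "including treatment group as a fixed effect and baseline VAP-1/SSAO activity or methylamine concentration as a covariate".

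The general rule in SAP 8.1 mentions baseline only: "The corresponding baseline value will be used as a covariate in the model". The protocol's own MMRM (9.4.3.2) is a "model with treatment group, visit, and treatment group by visit interaction as factors and baseline value as covariate". SAP Section 11 reports added exploratory endpoints and no change of model terms.

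**The concern.** The SAP adjusts an endpoint for the randomization stratum in one model and not in another, and does not say why. Percent change in VAP-1/SSAO activity, a secondary endpoint, is modelled with the stratum in 8.8.3 and without it in 8.8.4.4. Each endpoint listed in 8.10.8 is in the same position. A programmer who follows the text literally will report two treatment differences per endpoint that are adjusted differently, and the choice between them is left until the results are known.

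There is also a precision argument. Stratified randomization balances the factor between arms, so the true variance of the treatment difference largely excludes the factor's contribution. A model that leaves the factor out keeps that contribution in its residual variance. If the factor predicts outcome, the reported standard errors are then too large. Protocol 8.1.9 describes cT1 as correlated with histological activity, fibrosis and PDFF. That makes a prognostic stratum plausible, but these are cross-sectional associations and do not show that it predicts change once baseline is in the model.

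**Working it through.** The plan states no SD, interval width or power for these analyses, so there is no figure to reproduce. The check has two parts.

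**1. Model terms side by side**

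| Model | Outcomes | Baseline | cT1 stratum |
|---|---|---|---|
| ANCOVA, 8.8.3 | Change and percent change, VAP-1/SSAO activity and methylamine | yes | yes |
| MMRM, 8.8.4.4 | The same variables | yes | no |
| ANCOVA, 8.10.1.1 and reuse | cT1, MRI-PDFF, stiffness, LFTs, biomarkers | yes | yes |
| MMRM, 8.10.8 | ALT, AST, GGT, cT1, MRI-PDFF, CK-18, PRO-C3, C3M and their ratio | yes | no |
| ANCOVA, 8.8.4.3 | A_avg, A_min, C_avg, C_max, sub-study only | yes | no |

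Rows 1 and 2 share endpoints, as do rows 3 and 4. Row 5 analyses different variables.

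**2. Effect on the 95% interval**

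Inputs from the documents:

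- Full study: 20 per dose at three doses plus 20 pooled placebo, N = 80.
- Sub-study, both parts: 8 + 6 + 6 active and 4 + 3 = 7 placebo, N = 27.
- Sub-study, Part 1 only: 8 active and 4 placebo, N = 12.

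Assumed, not in the documents: the partial R² of the stratum given treatment and baseline, and strata split evenly and balanced within arms. The calculation is for an ANCOVA at one visit; the MMRM itself was not simulated.

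Width with the stratum divided by width without it:

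ratio = √(1 − R²) × t(0.975, df − 1) / t(0.975, df)

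Residual df without the stratum are 80 − 5 = 75, 27 − 5 = 22 and 12 − 3 = 9. The t quantiles go from 1.992 to 1.993, from 2.074 to 2.080, and from 2.262 to 2.306.

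| Partial R² | N = 80 | N = 27 | N = 12 |
|---|---|---|---|
| 0 | 1.000 | 1.003 | 1.019 |
| 0.02 | 0.990 | 0.993 | 1.009 |
| 0.05 | 0.975 | 0.977 | 0.994 |
| 0.10 | 0.949 | 0.951 | 0.967 |
| 0.20 | 0.895 | 0.897 | 0.912 |

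For example, N = 80 and R² = 0.10 give √0.90 × 1.993/1.992 = 0.949.

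Below the break-even R², 1 − (t_df / t_(df−1))², adding the stratum widens the interval. From unrounded quantiles this is about 0.0004 at N = 80, 0.006 at N = 27 and 0.038 at N = 12.

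Simulation with 4,000 replicates per setting agrees. At N = 80, a stratum effect of 0.5 residual SD gave a mean-width ratio of 0.969. The implied R² is 0.0625/1.0625 = 0.059, for which the formula gives 0.970. With a weak effect of 0.25 residual SD, the interval narrowed in only 38% of replicates at N = 27 and 31% at N = 12. For cT1, taking the stratum as a split of the baseline covariate with no further effect, the ratio at N = 80 was 1.007, slightly wider.

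**The case against.** The case for leaving the models alone has substance.

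- **The MMRM matches the protocol.** Its four terms are those of protocol 9.4.3.2, and SAP 8.1 names only baseline. This is true, but the protocol's ANCOVA in the same section has no stratum either, and the SAP adds it there. Conformity with the protocol therefore does not explain why one model was extended and the other was not.
- **Little depends on it.** All testing is nominal and exploratory, the sample size was set without regard to power, and the dose-response analysis is conditional on Part 2 enrolling. This stands and keeps the point minor.
- **No bias.** Among patients randomized together, omitting the stratum does not bias the treatment difference; at worst the standard errors are conservative. This stands too. Pooling placebo across parts and comparing doses between parts lies outside that protection, but the documents give no cT1 mix by part, so no bias is claimed.
- **The sub-study is very small.** With as few as 4 placebo patients, a simpler model in 8.8.4.3 is defensible. This stands, but the SAP does not give it as the reason.

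Two stronger readings are tempting. A reader might infer that the intervals are demonstrably and avoidably wide. The documents give no association between the stratum and any outcome after baseline adjustment, so a gain is possible but not shown. A reader might also infer that 8.8.4.3 gives conflicting estimates for the endpoints of 8.8.3. It does not: it analyses profile parameters in sub-study patients only. Even for the MMRM, its estimates would differ somewhat from the ANCOVA's with identical covariates, so the stratum would not account for all of any difference.

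**Conclusion.** The omission and the inconsistency are established by the text: 8.8.4.4, and through it 8.10.8, leaves out a stratification factor that the SAP's ANCOVAs of the same endpoints include, with no stated reason.

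The effect on precision is conditional and modest. At N = 80 the 95% interval with the stratum would be 0% to about 5% narrower for an assumed partial R² of 0 to 0.10, with essentially no gain for cT1. This rests on the assumed R², evenly split and balanced strata, and a single-visit ANCOVA standing in for the MMRM. In 8.8.4.3 the direction is uncertain: over the same R² range the interval changes from about 2% wider to 3% narrower at N = 12, and from 0.3% wider to about 5% narrower at N = 27.

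This is a worthwhile tidy-up, not a threat to the study's conclusions.

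**What to change.** In SAP 8.8.4.4, add the cT1 randomization stratum (two levels, split at 900 ms) to the list of fixed effects; 8.10.8 inherits it. Record in Section 11 that this adds a term to the protocol's MMRM.

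In 8.8.4.3, either add the stratum or state that it is left out because of the small sub-study sample.

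The cost is a line or two of SAP text and one degree of freedom: 75 to 74 in the single-visit calculation at N = 80. If the stratum is added in 8.8.4.3, residual df fall from 22 to 21 with both parts, or from 9 to 8 with Part 1 alone. Making the change before unblinding removes any later choice between two adjusted estimates.

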### 8.9. Exposure Response Analyses

The plasma PK parameters  $AUC_{tau}$ ,  $C_{max}$ , and  $C_{tau}$  will be used to evaluate exposure-response. PK parameters will be set to 0 for the placebo group for the purpose of PK/PD.

Pharmacodynamic exposure-response analyses of plasma VAP-1/SSAO activity and methylamine concentration PD parameters will be performed using several exposure-response models for the PK/PD Analysis Set, including but not limited to linear, quadratic, exponential, and  $E_{max}$ . The best fit significant model will be chosen based on AIC, the smaller the AIC value the better the model fit.

Additional exposure-response and dose-response (as applicable) analyses may be explored for baseline patient characteristics such as sVAP-1, BMI, diabetes mellitus, or other characteristics or additional efficacy, safety, and PD endpoints, as needed. These analyses will be described in a separate document.

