Coagulation ^d	X	X								Specific analytes are listed in Appendix 1 . PT/INR will be tested at Screening, Week 0, and if significant abnormal liver function tests are observed.
Fasting Lipid Profile ^d		X			X		X	X		Specific analytes are listed in Appendix 1 .
Serology	X									Includes HBsAg, anti-HCV, and anti-HIV.

	Screening	Treatment Period ^a						ET ^b	Follow-Up ^c	Notes
Visit	Screening	Week 0	Week 2	Week 4	Week 6	Week 8	Week 12		Week 16	
Study Day	-42 to Day -1	Day 1	15	29	43	57	85		113	Visit windows post-randomization through Week 12: \pm 3 days from the specified study day. Visit window Week 16: 1 week prior/+2 days from the specified study day.
COVID-19 Assessment ^{d,e}	X	X			X		X			Screening and on-study COVID-19 assessments should be conducted in accordance with Appendix 8 .
Serum pregnancy test ^d	X	X		X		X	X	X		WOCBP only.
Serum FSH	X									To confirm postmenopausal status, as outlined in Appendix 7 .
Blood Alcohol Test	X									
Urinalysis ^d	X	X			X		X	X	X	Specific analytes are listed in Appendix 1 . Microscopic examination is required if blood or protein is abnormal.
Urine Drug Screen ^d	X	X		X		X	X	X	X	
Total Urine Collection (PK/PD Sub-Study only)		X			X					Total urine collection from 0-8 hours post dose as specified in Appendix 2 .
Intensive PK and PD Sampling (PK/PD Sub-Study only)		X			X		X			Intensive PK sampling will be performed pre-dose and 0.5, 1, 2, 4, 6, 8 and 24 hours after the first dose of study drug on Week 0/Day 1 and Week 6, and at pre-dose and 0.5, 1, 2, 4, 6, 8, 24, 48 and 72 hours after the last dose of study drug at Week 12. Refer to Appendix 2 for additional detail.

	Screening	Treatment Period ^a						ET ^b	Follow-Up ^c	Notes
Visit	Screening	Week 0	Week 2	Week 4	Week 6	Week 8	Week 12		Week 16	
Study Day	-42 to Day -1	Day 1	15	29	43	57	85		113	Visit windows post-randomization through Week 12: \pm 3 days from the specified study day. Visit window Week 16: 1 week prior/+2 days from the specified study day.
Trough PK and PD Sampling ^d		X	X	X	X	X	X	X		Only one sample will be collected at each visit prior to drug administration on the visit day. Patients discontinuing the study at any time for any reason will have one sample collected at the ET visit. Refer to Appendix 2 for additional detail.
Baseline sVAP-1 ^f		X								
NASH/Fibrosis Biomarkers ^d		X			X		X	X		Includes CK-18 (M30 and M65), PIIINP, TIMP-1, HA, PRO-C3, and C3M.
Inflammation Biomarkers ^d		X	X	X	X	X	X	X		Includes hs-CRP, IL-6, ICAM-1, and VCAM-1.

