Plasma exposures to TERN-201 were greater than dose proportional. TERN-201 was rapidly cleared from plasma. Steady state was achieved in the highest dose group (10 mg) after Day 7 of dosing. The half-life of TERN-201 increased with dose, suggesting saturable, target-mediated clearance.

Single and multiple doses of TERN-201 significantly suppressed plasma total amine oxidase activity at all doses studied. Using an exploratory assay to assess the effect of TERN-201 on VAP-1/SSAO-specific amine oxidase activity in the plasma, near complete inhibition (>80% with 1 mg, > 90% with 10 mg) was observed after only a single dose on Day 1 (achieved within 4 hours after dosing) with sustained suppression over the dosing period in MAD cohorts. Dose-dependent increases in methylamine, an endogenous substrate of VAP-1/SSAO predicted to increase upon VAP-1/SSAO inhibition, were observed after the first dose of TERN-201 and continued to increase in a dose-dependent manner after multiple doses of TERN-201.

Based on the exploratory assessment on plasma PK of two TERN-201 metabolites, TRN-001021 and TRN-001744, the percentages of either metabolite AUC relative to the total TERN-201-related plasma AUC (sum of TERN-201, TRN-001021, and TRN-001744) were calculated. Median TRN-001021 AUC was <10% and 13.7% of the total plasma AUC associated with TERN-201 in the 4 mg and 10 mg groups, respectively. Median TRN-001744 AUC was 11.5% and <10% of the total plasma AUC associated with TERN-201 in the 4 mg and 10 mg groups, respectively.

Additional details on Study TERN201-US-A101 are available in the Investigator's Brochure.

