For continuous variables, the number of patients, mean, standard deviation (SD), median, 25th (Q1) and 75th (Q3) percentiles, minimum, and maximum values will be presented. The precision of summary statistics, unless otherwise specified will be as follows: mean, median, Q1, and Q3 to 1 more decimal place than the raw data, SD to 2 decimal places more than the raw data, and minimum and maximum to the same decimal places as the raw data. In general, the number of decimal places should not exceed 3 decimal places unless appropriate.

For log-normal data (e.g., the PK parameters of area under the concentration-time curve [AUC] and maximum observed concentration [Cmax]), the geometric mean and geometric coefficient of variation (CV%) will also be presented. The precision of descriptive statistics will be as follows: mean, median, Q1, and Q3 to 1 more decimal place than the raw data, SD to 2 decimal places more than the raw data, the minimum and maximum to the same number of decimal places as the raw data, geometric mean to 3 significant figures, and geometric CV% to 1 decimal place. The PK parameters Tmax, Tmin, Tlast, and t1/2 will be presented to 1 decimal place and all other plasma and urine PK parameters will be presented to 3 significant figures.

Confidence intervals (CIs) will be provided and will be rounded to 1 decimal place, unless otherwise specified, in the table and listing shell. A full set of summary statistics will only be presented if 3 or more values are available. If there are less than 3 values, only the min, max, and N will be presented. The other summary statistics will be denoted as not calculated (NC).

For tables where rounding is required, rounding will be done to the nearest round-off unit. For example, when rounding to the nearest integer, values  $\geq$ XX.5 will be rounded up to XX+1 (e.g., 97.5 will round up to 98), while values <XX.5 will be rounded down to XX (e.g., 97.4 will round down to 97).

All statistical tests comparing groups will be conducted at the 2-sided, 0.05 level of significance, unless otherwise specified. Summary statistics for each treatment group will be presented, as well as two-sided 90% and 95% CIs comparing groups will be provided.

Other general programming specifications are provided in [Appendix 1](#).

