## **8.6. Multiple Comparisons/Multiplicity**

There will be no adjustment for multiplicity. Statistical testing will be considered nominal, descriptive and exploratory.

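### SAP 8.9 puts placebo at zero exposure and gives no exposure estimate among treated patients, so a significant exposure-response model shows drug versus placebo, not dependence on exposure

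*SAP*

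**What the plan says.** SAP 8.9 uses AUCtau, Cmax and Ctau as exposure measures and sets them to zero for placebo: "PK parameters will be set to 0 for the placebo group for the purpose of PK/PD". The candidate models are "including but not limited to linear, quadratic, exponential, and" Emax. The selection rule is: "The best fit significant model will be chosen based on AIC, the smaller the AIC value the better the model fit". What counts as significant is not defined there. SAP 4.1 has a general rule, "All statistical tests comparing groups will be conducted at the 2-sided, 0.05 level of significance, unless otherwise specified", and SAP 8.6 adds that "Statistical testing will be considered nominal, descriptive and exploratory".

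Plasma PK and PD parameters are computed for PK/PD sub-study patients only (SAP 8.7.4 and 8.8.4). SAP 8.9 names a PK/PD Analysis Set; SAP Table 5 has no set of that name and lists PK/PD Substudy.

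On the expected effect, Protocol 2.2.2 reports from the first-in-human study that "near complete inhibition (>80% with 1 mg, > 90% with 10 mg) was observed after only a single dose on Day 1". SAP 8.9 plans no treated-only fit, no drug/placebo indicator and no test of the slope among treated patients.

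**The concern.** At the first-in-human level of inhibition, placebo patients form a cluster at zero exposure and about zero effect, and treated patients form a second cluster at non-zero exposure and near-maximal inhibition. Any curve through both clusters beats a flat line because the drug works. The test cannot separate that from response rising with exposure among those who take the drug.

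The drug-versus-placebo question is already answered by the ANCOVA in SAP 8.8.3 and 8.8.4.3. Exposure-response is a separate stated exploratory objective and endpoint. At stake is whether SAP 8.9 gives a result that answers it, and whether the word significant beside a fitted curve will be read as evidence that it does.

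**Working it through.** The documents give no power, error rate or variance for this analysis, so there is no planned figure to reproduce. I checked what the rule does when the true response is the same at every treated exposure.

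**Inputs from the documents**
- Part 1 sub-study: 8 active (10 mg) and 4 placebo (SAP 2.2).
- Part 2 sub-study: 6 per dose level and 3 placebo (SAP 2.2). With both doses, Parts 1 and 2 give 8 + 6 + 6 = 20 active and 4 + 3 = 7 placebo.
- Effect on VAP-1/SSAO: a flat change of -80 or -90 points, from Protocol 2.2.2.
- Level: two-sided 0.05, borrowed from SAP 4.1.

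**Assumptions**
- SD of percent change 10 to 30 points.
- Lognormal exposure with CV 30 to 100%.
- Median exposure proportional to dose^1.3. Protocol 2.2.2 says only that exposure was more than dose proportional.

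**Why the test is drug versus placebo.** The standard error of the contrast is SD × √(1/n_active + 1/n_placebo).
- 8 and 4: factor √(0.125 + 0.25) = 0.612. For 90 points and SD 30, 90/(30 × 0.612) = 4.9, against a critical t of 2.23 on 10 df.
- 20 and 7: factor √(0.05 + 0.143) = 0.439. The ratio is 90/(30 × 0.439) = 6.8, against 2.06 on 25 df.

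**Simulation of the full rule.** I fitted:
- linear, a + bx
- quadratic, a + bx + cx²
- exponential, a + b(exp(x/k) − 1)
- Emax, E0 + Emax·x/(EC50 + x)

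Each was compared with an intercept-only model by F test at 0.05. The smallest AIC among the significant models was kept.

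| Flat true effect | Significant model kept, Part 1 (8:4) | Significant model kept, Parts 1+2 (20:7) |
|---|---|---|
| -90 points, SD 10-30, CV 30-100% | 96-100% | 100% |
| -80 points, SD 10-30, CV 50% | 94-100% | 99.9-100% |
| 2 SD | 71-79% | 97-98% |
| 1 SD | 25-32% | 48-51% |
| none | 7-10% (both designs) | 7-10% (both designs) |

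Raw activity values instead of percent change gave 98 to 100%. Protocol 6.4 gives a 6:6 split for Part 1 where other sections give 8:4; at -90 points, 6:6 gave 98 to 100%.

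**Which curve is kept.** With both parts at 80 to 90 points, Emax is selected in 99 to 100% of runs. With Part 1 alone and exposure CV 50%:

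| Effect, SD | Linear or quadratic | Emax |
|---|---|---|
| -80, SD 10 | 10% | 90% |
| -80, SD 20 | 29% | 71% |
| -80, SD 30 | 42% | 51% |
| -90, SD 20 | 22% | 77% |

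Over the whole Part 1 grid at -90 points, a linear or quadratic curve is kept in about 0 to 62% of runs. The top of that range is at SD 30 and CV 30%, where Emax falls to about 97 − 62 = 35%.

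**Treated patients only, same flat effect.** The linear slope is significant in about 4 to 8% of runs. Some model among the four is significant in about 7 to 11%; the excess over 5% comes from testing four shapes. A drug/placebo indicator with a common variance gave 3 to 7% for percent change with equal SDs. It fell to 0 to 1% when placebo was more variable than active, because placebo variance inflates the slope's standard error.

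**The case against.** The strongest case against runs as follows.

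1. **Zero is placebo's true exposure.** Including placebo supports the estimate of E0. If the drug works, response does differ between zero and non-zero exposure, so rejecting a flat line is not in itself an error. This stands: the fault is in what significance can be taken to mean.
2. **AIC usually picks a curve that shows the plateau.** With 92% inhibition (SD 3), placebo SD 10 and exposure CV 40 to 60%, Emax was chosen in 98 to 100% of Part 1 runs and 100% with both parts. The chosen curve rose by a median of only 0.1 to 0.4 points between the 10th and 90th percentiles of treated exposure. A reader might infer that the plan will wrongly show more exposure adding effect. That does not hold with both parts. It is a risk mainly with Part 1 alone at larger SD, or with weaker effects.
3. **The SAP has no rule that declares exposure-response.** A reader might infer that it would declare one almost every time. SAP 8.9 selects a curve, and SAP 8.6 makes testing nominal and exploratory. This stands, although the selected model still carries the label significant with nothing beside it to say what was shown.
4. **The flat premise is hypothetical.** The first-in-human figures differ between 1 mg and 10 mg, methylamine rose with dose, the assay was exploratory, and Protocol 4.3 warns that the effect in NASH patients may differ. This stands. The simulation shows what the rule cannot distinguish; it does not predict a flat response.
5. **Dose-response is covered elsewhere.** SAP 8.8.4.4 compares doses pairwise and by MMRM, but it depends on Part 2 enrolling and concerns dose, not exposure. Nor do the documents make the SAP 8.9 model a basis for opening Part 2; that rests on the Week 6 review of safety, PK and PD.

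A reader might also infer a clear loss from using the sub-study only, since all patients give trough samples ("Only one sample will be collected at each visit prior to drug administration on the visit day"). Going from 20 to 60 treated patients would cut a standard error by √(60/20) = 1.7. That gain is unproven: Protocol 2.2.2 calls TERN-201 rapidly cleared, so many troughs may be unquantifiable, and SAP 8.7.4 already allows population PK on sparse samples.

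**Conclusion.** The point holds in a limited form. For VAP-1/SSAO at the first-in-human effect size, significance of the model kept under SAP 8.9 restates drug versus placebo. A response flat across treated exposures passes in about 94 to 100% of trials, against 4 to 8% for a treated-only slope. For flat effects of 1 to 2 SD the rule passes in about 25 to 79% (Part 1) and 48 to 98% (both parts). The documents give no methylamine effect size, so no rate can be attached to that marker.

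A misleading trend in the selected curve is a narrower problem: up to about 50 to 60% with Part 1 alone and a large SD, and close to nil with both parts at this effect size. The rates rest on assumed SDs, exposure CVs and a flat truth. The main conclusion held over every SD and CV tried and under either Part 1 split. The analysis is exploratory, so this is a gap in answering a stated objective, not a threat to the primary safety analysis.

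**What to change.** In SAP 8.9:

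- Keep the placebo-inclusive fit for E0 and curve shape. Define the significance test, and state that a significant result shows a drug-versus-placebo difference only.
- Add one prespecified model in TERN-201 patients. Report the exposure slope with its confidence interval, and base any statement that response varies with exposure on that term. A drug/placebo indicator in the pooled model is an alternative if placebo and active have separate variances.
- Prespecify one shape (linear is enough) for that term, so that trying four shapes does not inflate the 5% level.
- Use the analysis-set name in SAP Table 5.
- Optionally, add a descriptive Ctau model in all treated patients if enough troughs are quantifiable. Its response would be trough PD, since PD parameters exist only in the sub-study.

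Dropping the word significant from the selection rule would gain little, because some curve would then always be kept.

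The cost is a few sentences, one more fit, and fewer results that look significant. With Part 1 alone the slope will be imprecise: 8 patients at one dose, SD 20 and exposure CV 50% give a standard error of about 20/(0.5 × √7) = 15 points per change of one mean exposure, so a 95% half-width of about 2.45 × 15 = 37 points. Reporting that width is more informative than a significant pooled curve.
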